**Boehringer Ingelheim**

BI Trial No.: 1399-0001

c15848245-03

## Trial Protocol

19 Feb 2018

Page 4 of 82

Proprietary confidential information © 2018 Boehringer Ingelheim International GmbH or one or more of its affiliated companies

**16.1.1 Protocol and amendments**

---

Proprietary confidential information © 2018 Boehringer Ingelheim International GmbH or one or more of its affiliated companies

**Boehringer Ingelheim**

**BI Trial No.: 1399-0001**

**c15848245-03**

**Trial Protocol**

**19 Feb 2018**

**Page 5 of 82**

---

Proprietary confidential information © 2018 Boehringer Ingelheim International GmbH or one or more of its affiliated companies

**16.1.1 Protocol and amendments**

Proprietary confidential information © 2018 Boehringer Ingelheim International GmbH or one or more of its affiliated companies

**Boehringer Ingelheim  
BI Trial No.: 1399-0001  
c15848245-03**

**Trial Protocol**

**19 Feb 2018**

**Page 6 of 82**

Proprietary confidential information © 2018 Boehringer Ingelheim International GmbH or one or more of its affiliated companies

**16.1.1 Protocol and amendments**

Proprietary confidential information © 2018 Boehringer Ingelheim International GmbH or one or more of its affiliated companies

**Boehringer Ingelheim  
BI Trial No.: 1399-0001  
c15848245-03**

**16.1.1 Protocol and amendments**

Proprietary confidential information © 2018 Boehringer Ingelheim International GmbH or one or more of its affiliated companies

**Boehringer Ingelheim  
BI Trial No.: 1399-0001  
c15848245-03**

**16.1.1 Protocol and amendments**

Proprietary confidential information © 2018 Boehringer Ingelheim International GmbH or one or more of its affiliated companies

**Boehringer Ingelheim  
BI Trial No.: 1399-0001  
c15848245-03**

**Trial Protocol**

**19 Feb 2018**

**Page 10 of 82**

Proprietary confidential information © 2018 Boehringer Ingelheim International GmbH or one or more of its affiliated companies

**ABBREVIATIONS**

AE	Adverse event
AESI	Adverse events of special interest
AMG	Arzneimittelgesetz (German drug law)
ANCOVA	Analysis of covariance

AUCt1-t2 Area under the concentration-time curve of the analyte in plasma over the time interval t1 to t2

BI	Boehringer Ingelheim
b.i.d.	Bis in die , twice daily
BLQ	Below limit of quantification
BMI	Body mass index (weight divided by height squared)
BP	Blood pressure
CA	Competent authority
CF	Cystic fibrosis
CI	Confidence interval

Cmax Maximum measured concentration of the analyte in plasma

COPD	Chronic obstructive pulmonary disease
CRF	Case report form
CTP	Clinical trial protocol
CTR	Clinical trial report
CV	Arithmetic coefficient of variation
DILI	Drug induced liver injury
ECG	Electrocardiogram
EDTA	Ethylenediaminetetraacetic acid

**16.1.1 Protocol and amendments**

Proprietary confidential information © 2018 Boehringer Ingelheim International GmbH or one or more of its affiliated companies

**Boehringer Ingelheim  
BI Trial No.: 1399-0001  
c15848245-03**

**Trial Protocol**

**19 Feb 2018**

**Page 11 of 82**

Proprietary confidential information © 2018 Boehringer Ingelheim International GmbH or one or more of its affiliated companies

**EOT** End of trial

**gCV** Geometric coefficient of variation

**gMean** Geometric mean

**HR** Heart rate

**IB** Investigator's brochure

**IEC** Independent Ethics Committee

**IRB** Institutional Review Board

**ISF** Investigator site file

**LC-MS/MS** Liquid chromatography with tandem mass spectrometry

**MedDRA** Medical Dictionary for Regulatory Activities

**NC** Not calculated

**NOA** Not analysed

**NOAEL** No observed adverse effect level

**NOR** No valid result

**NOS** No sample available

**NOTEI** No toxic effect level

**PK** Pharmacokinetic(s)

**PKS** Pharmacokinetic set

**PR** Pulse rate

**q.d.** *Quaque die*, once daily

**QT** Time between start of the Q-wave and the end of the T-wave in an electrocardiogram

**QTc** QT interval corrected for heart rate using the method of Fridericia (QTcF) or Bazett (QTcB)

**RDC** Remote data capture

**REP** Residual effect period

**SAE** Serious adverse event

**SCR** Screening

**SRD** Single-rising dose

**SUSAR** Suspected Unexpected Serious Adverse Reaction

**16.1.1 Protocol and amendments**

---

Proprietary confidential information © 2018 Boehringer Ingelheim International GmbH or one or more of its affiliated companies

**Boehringer Ingelheim****BI Trial No.: 1399-0001****c15848245-03****Trial Protocol****19 Feb 2018****Page 12 of 82**

---

Proprietary confidential information © 2018 Boehringer Ingelheim International GmbH or one or more of its affiliated companies

TMF

Trial master file

TDMAP

Trial Data Management and Analysis Plan

TSAP

Trial statistical analysis plan

ULN

Upper limit of normal

**16.1.1 Protocol and amendments**

---

Proprietary confidential information © 2018 Boehringer Ingelheim International GmbH or one or more of its affiliated companies

**Boehringer Ingelheim**

**BI Trial No.: 1399-0001**

**c15848245-03**

**Trial Protocol**

**19 Feb 2018**

**Page 13 of 82**

---

Proprietary confidential information © 2018 Boehringer Ingelheim International GmbH or one or more of its affiliated companies

**Boehringer Ingelheim**

**BI Trial No.: 1399-0001**

**c15848245-03**

**Trial Protocol**

**19 Feb 2018**

**Page 14 of 82**

**Boehringer Ingelheim**

**BI Trial No.: 1399-0001**

**c15848245-03**

**Trial Protocol**

**19 Feb 2018**

**Page 15 of 82**

Proprietary confidential information © 2018 Boehringer Ingelheim International GmbH or one or more of its affiliated companies

**Boehringer Ingelheim**

**BI Trial No.: 1399-0001**

**c15848245-03**

**Trial Protocol**

**19 Feb 2018**

**Page 16 of 82**

Proprietary confidential information © 2018 Boehringer Ingelheim International GmbH or one or more of its affiliated companies

**Boehringer Ingelheim**

**BI Trial No.: 1399-0001**

**c15848245-03**

**Trial Protocol**

**19 Feb 2018**

**Page 17 of 82**

**Boehringer Ingelheim**

**BI Trial No.: 1399-0001**

**c15848245-03**

**Trial Protocol**

**19 Feb 2018**

**Page 18 of 82**

**Boehringer Ingelheim**

**BI Trial No.: 1399-0001**

**c15848245-03**

**Trial Protocol**

**19 Feb 2018**

**Page 19 of 82**

**Boehringer Ingelheim**

**BI Trial No.: 1399-0001**

**c15848245-03**

**Trial Protocol**

**19 Feb 2018**

**Page 20 of 82**

**Boehringer Ingelheim**

**BI Trial No.: 1399-0001**

**c15848245-03**

**Trial Protocol**

**19 Feb 2018**

**Page 21 of 82**

Proprietary confidential information © 2018 Boehringer Ingelheim International GmbH or one or more of its affiliated companies

**Boehringer Ingelheim**

**BI Trial No.: 1399-0001**

[figure not shown]
**c15848245-03**

**Trial Protocol**

**19 Feb 2018**

**Page 22 of 82**

Proprietary confidential information © 2018 Boehringer Ingelheim International GmbH or one or more of its affiliated companies

**Boehringer Ingelheim****BI Trial No.: 1399-0001****c15848245-03****Trial Protocol****19 Feb 2018****Page 23 of 82**

**16.1.1 Protocol and amendments**

Proprietary confidential information © 2018 Boehringer Ingelheim International GmbH or one or more of its affiliated companies

**Boehringer Ingelheim****BI Trial No.: 1399-0001****c15848245-03****Trial Protocol****19 Feb 2018****Page 24 of 82**

Proprietary confidential information © 2018 Boehringer Ingelheim International GmbH or one or more of its affiliated companies

**2.2 TRIAL OBJECTIVES**

The primary objective of this trial is to investigate the safety and tolerability of BI 1265162 in healthy male subjects following inhalative administration of single rising doses.

Secondary objective is the exploration of the pharmacokinetics (PK) of BI 1265162 after single dosing.

**16.1.1 Protocol and amendments**

---

Proprietary confidential information © 2018 Boehringer Ingelheim International GmbH or one or more of its affiliated companies

**Boehringer Ingelheim**

**BI Trial No.: 1399-0001**

**c15848245-03**

**Trial Protocol**

**19 Feb 2018**

**Page 25 of 82**

Proprietary confidential information © 2018 Boehringer Ingelheim International GmbH or one or more of its affiliated companies

A description of the endpoints to be determined, and the observations along with specific information as how to collect the data for that information, is provided in [Section 5](#).

**Boehringer Ingelheim**

**BI Trial No.: 1399-0001**

**c15848245-03**

**Trial Protocol**

**19 Feb 2018**

**Page 26 of 82**

**Boehringer Ingelheim**

**BI Trial No.: 1399-0001**

**c15848245-03**

**Trial Protocol**

**19 Feb 2018**

**Page 27 of 82**

**16.1.1 Protocol and amendments**

Proprietary confidential information © 2018 Boehringer Ingelheim International GmbH or one or more of its affiliated companies

**Boehringer Ingelheim  
BI Trial No.: 1399-0001  
c15848245-03**

**Trial Protocol**

**19 Feb 2018**

**Page 28 of 82**

Proprietary confidential information © 2018 Boehringer Ingelheim International GmbH or one or more of its affiliated companies

**3. DESCRIPTION OF DESIGN AND TRIAL POPULATION**

**3.1 OVERALL TRIAL DESIGN AND PLAN**

This single-rising dose trial is designed as single-blind, partially randomised, and placebo-controlled within parallel dose groups.

Partially randomised means that the subjects will be treated in two equally sized cohorts per dose group, with the first cohort being treated in a fixed sequence and the second cohort being treated in a randomised order.

A total of 56 healthy male subjects is planned to participate in the trial, according to 7 sequential groups comprising 8 subjects per group. However, additional subjects may be entered to allow testing of intermediate doses within the planned and approved dose range on the basis of experience gained during trial conduct (e.g. preliminary PK data), i.e. the actual number of subjects entered may exceed 56. Such changes may be implemented via non-substantial CTP Amendments.

Within each dose group, 6 subjects will receive the active drug and 2 will receive placebo. Only one dose is tested within each dose group

The dose groups to be evaluated are outlined in [Table 3.1: 1](#) below.

---

---

---

On the first study day of each dose level, the first cohort will be treated in the following order: first subject (active) followed at least 1 h later by the second subject (placebo) followed at least 1 h later by the third subject (active) followed at least 10 min later by the fourth subject (active). If BI 1265162 treatment is safe and showed acceptable tolerability in the first cohort, the subjects in the second cohort will be treated not earlier than 2 days later than the first treated volunteer in the first cohort. In the second cohort, a time interval of at least 10 min will be maintained between dosing of individual subjects in a random order. The dose groups will be investigated consecutively in ascending order of doses. A time interval of at least 6 days will be maintained between the administration of the study drug to the first cohort in a dose group and the first cohort in the next dose group. The decision to proceed to the next dose group will be based upon the safety, tolerability data of the preceding dose groups and explorative PK data in some dose groups (see [Section 7.3.4](#)).

### **16.1.1 Protocol and amendments**

Proprietary confidential information © 2018 Boehringer Ingelheim International GmbH or one or more of its affiliated companies

**Boehringer Ingelheim  
BI Trial No.: 1399-0001  
c15848245-03**

**Trial Protocol**

**19 Feb 2018**

**Page 29 of 82**

Proprietary confidential information © 2018 Boehringer Ingelheim International GmbH or one or more of its affiliated companies

The next dose will only be given if, in the opinion of the investigator, no safety concerns arose in the preceding dose group (i.e. no dose-limiting events occurred) and if none of the pre-specified trial-specific stopping criteria were met (refer to [Section 3.3.4.2](#)).

A documented Safety Review must take place prior to each dose escalation. Furthermore, an unscheduled safety review meeting can be requested anytime for any reasonable cause by the Principal Investigator (or an authorised deputy) or the sponsor of the study, e.g. because of any unforeseen adverse events, etc. Dose escalation will only be permitted if no safety concerns exist in the opinion of the Principal Investigator (or an authorised deputy) and the Trial Clinical Monitor (or an authorised deputy).

The minimum data set for review consists of the following data:

- AEs in the current and preceding dose groups up to at least 48h post dosing (including clinically relevant findings from ancillary safety testing listed below) (Note: AEs may be ongoing at the time of Safety Reviews and AE information may be subject to change prior to Database Lock)
- Results from 12-lead ECG and continuous ECG monitoring in the current and preceding dose groups.
- Vital signs in the current and preceding dose groups
- Clinical laboratory tests in the current and preceding dose groups
- Preliminary PK data as per [Section 7.3.4](#)
- Check of criteria for stopping subject treatment as per [Section 3.3.4.1](#)

The decision to escalate the dose will be made jointly by the Principal Investigator (or an authorised deputy) and the Trial Clinical Monitor (or an authorised deputy) after in-depth analysis of all available safety data, especially SAEs (if occurred), AEs and out-of-range laboratory results (if considered clinically significant). Safety Reviews can be conducted face-to-face or by video/telephone conference. The Trial Clinical Monitor is responsible for organization and minutes of the reviews. Minutes will be signed off by the Principal Investigator (or an authorised deputy) and filed in the ISF and TMF.

The investigator (after consultation with the sponsor) is allowed to alter the scheduled dose levels (e.g. add low and/or intermediate dose levels) on the basis of experience gained during the study, provided the planned and approved highest dose is not exceeded. In this case, the total number of subjects in this trial might increase. The investigator and/or the sponsor should stop dose escalation in case the safety evaluation leads to concerns that would not allow higher dosing.

An overview of all relevant trial activities is provided in the [Flow Chart](#). For visit schedules and details of trial procedures at selected visits, refer to [Sections 6.1](#) and [6.2](#), respectively.

#### **3.1.1      Administrative structure of the trial**

The trial is sponsored by Boehringer Ingelheim (BI) Pharma GmbH & Co. KG, Germany.

**16.1.1 Protocol and amendments**

Proprietary confidential information © 2018 Boehringer Ingelheim International GmbH or one or more of its affiliated companies

**Boehringer Ingelheim  
BI Trial No.: 1399-0001  
c15848245-03**

**Trial Protocol**

**19 Feb 2018**

**Page 30 of 82**

Proprietary confidential information © 2018 Boehringer Ingelheim International GmbH or one or more of its affiliated companies

BI has appointed a Trial Clinical Monitor, responsible for coordinating all required activities, in order to

- manage the trial in accordance with applicable regulations and internal SOPs,
- direct the clinical trial team in the preparation, conduct, and reporting of the trial,
- ensure appropriate training and information of local clinical monitors (CML), Clinical Research Associates (CRAs), and participating trial sites.

The trial medication will be provided by the Clinical Trial Supplies Unit (CTSU), BI Pharma GmbH & Co. KG, Biberach, Germany.

The trial will be conducted at

under the supervision of the Principal

Investigator.

Safety laboratory tests will be performed by the local laboratory of the trial site (Medizinisches Versorgungszentrum [name], [name] & Partner, Kaiserslautern, Germany).

The analyses of BI 1265162 concentrations in plasma and urine will be performed at the Department of Drug Metabolism and Pharmacokinetics, BI Pharma GmbH & Co. KG, Biberach, Germany.

The digitally recorded 12-lead ECGs will be sent to a specialised contract research organisation ( ) for evaluation.

On-site monitoring will be performed by BI or a contract research organisation appointed by BI.

Data management and statistical evaluation will be done by BI or a contract research organisation appointed by BI according to BI SOPs.

Tasks and functions assigned in order to organise, manage, and evaluate the trial are defined according to BI SOPs. A list of responsible persons and relevant local information can be found in the ISF.

**3.2 DISCUSSION OF TRIAL DESIGN, INCLUDING THE CHOICE OF CONTROL GROUP**

For single -rising dose trials, the design described in [Section 3.1](#) is viewed favourable under the provision not to expose the subjects involved to undue risks since the main study objective is to investigate safety and tolerability of BI 1265162.

With the rising dose design, single-blind conditions regarding the subject's treatment (active or placebo) are maintained within each dose group. However, the current dose level will be known to subjects and investigators. The disadvantage of this trial design is a possible observer bias with regard to the dose-depending effects as well as time effects, but it has the virtue of minimizing subject risk by sequentially studying ascending doses. As time-effects

**16.1.1 Protocol and amendments**

Proprietary confidential information © 2018 Boehringer Ingelheim International GmbH or one or more of its affiliated companies

**Boehringer Ingelheim  
BI Trial No.: 1399-0001  
c15848245-03**

**Trial Protocol**

**19 Feb 2018**

**Page 31 of 82**

Proprietary confidential information © 2018 Boehringer Ingelheim International GmbH or one or more of its affiliated companies

are expected to be small relative to the differences between the doses in the broad range investigated, unbiased comparisons between treatments can still be expected.

It is standard in trials involving healthy volunteers to include a placebo group as control for the evaluation of safety and tolerability. Each dose group consists of 8 subjects with 6 on active treatment, and 2 on placebo. The placebo control group includes all subjects of all dose groups treated with placebo. 6 subjects per active treatment group are in general considered as sufficient for the exploratory evaluation of pharmacokinetics.

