**Trial Protocol**

**19 Feb 2018**

**Page 36 of 82**

Proprietary confidential information © 2018 Boehringer Ingelheim International GmbH or one or more of its affiliated companies

includes healthy subjects from a homogenous population, relevant imbalances between the dose groups are not expected.

The randomization list with study subject numbers and allocated treatments will be provided to the trial site and the sponsor (TCM) in advance. The allocation of subjects to study subject numbers will be performed prior to the first administration of trial medication. For this purpose, the subjects will be allocated to a study subject number by the method 'first come first served'. Once a subject number has been assigned, it cannot be reassigned to any other subject.

The randomisation procedure is described in [Section 7.5](#).

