### **4.1.5 Blinding and procedures for unblinding**

#### **4.1.5.1 Blinding**

The treatments administered (active or placebo) will be single-blind (blinded to subjects only). However, the current dose level will be known to the subjects.

Within the ECG laboratory, the staff involved with interval measurements and assessments will be blinded with respect to the treatment and also with regard to the recording date and time as well as the time points of the ECGs. The interval measurements for a given subject will be performed in a random and blinded sequence by a single technician. No more than two different blinded readers will evaluate the ECGs of the study.

In addition, the trial pharmacokineticist, trial pharmacometrist and bioanalyst may receive the randomisation codes prior to official unblinding to perform the interim / preliminary PK analysis. He or she will confirm in writing that the codes will be treated confidentially.

In addition, the drug metabolism scientist may receive the randomisation codes prior to official unblinding to perform metabolites in safety testing analysis (MIST). He or she will confirm in writing that the codes will be treated confidentially.

The database of this trial will be handled open-label, because no bias with regard to data cleaning of safety measures is expected.

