#### **4.1.5.2 Procedures for emergency unblinding**

As this trial will be conducted single-blinded, the treatment information will be known. Therefore, no emergency envelopes will be provided.

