**5.2 SAFETY****5.2.1 Endpoints of safety**

Primary endpoint to assess safety and tolerability of BI 1265162 is the number [N (%)] of subjects with drug-related adverse events.

Further criteria of interest:

- AEs (including clinically relevant findings from the physical examination)
- Safety laboratory tests
- 12-lead ECG
- Continuous ECG monitoring
- Vital signs (blood pressure, pulse rate)

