#### **Information required**

For each AE, the investigator should provide the information requested on the appropriate CRF pages and the BI SAE form (if applicable). The investigator should determine the causal relationship to the trial medication.

The following should also be recorded as an (S)AE in the CRF and BI SAE form (if applicable):

- Worsening of the underlying disease or of other pre-existing conditions
- Changes in vital signs, ECG, physical examination and laboratory test results, if they are judged clinically relevant by the investigator.

If such abnormalities already pre-exist prior to trial inclusion they will be considered as baseline conditions and should be collected in the CRF only.

All (S)AEs, including those persisting after individual subject's end of trial must be followed up until they have resolved, have been assessed as 'chronic' or 'stable', or no further information can be obtained.

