**7.5 RANDOMISATION**

The subjects of the first cohort per dose level will not be randomised to maintain a treatment sequence of active-placebo-active-active due to safety reasons. In the second cohort subjects will be randomised within each dose group in a 3:1 ratio, which reflects the ratio of subjects receiving active drug to placebo.

The sponsor will arrange for the randomisation as well as packaging and labelling of trial medication. The randomisation list will be generated using a validated system, which involves a pseudo-random number generator and a supplied seed number so that the resulting allocation is both reproducible and non-predictable.

The randomisation list will contain additional blocks to allow for subject replacement (refer to [Section 3.3.5](#)).

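### Must the protocol withdraw its expectation of unbiased comparisons because an unblinded investigator judges the primary endpoint?

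*Protocol*

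**What the plan says.** Section 3.2 of the protocol discusses the single-blind rising-dose design. It concedes: "The disadvantage of this trial design is a possible observer bias with regard to the dose-depending effects as well as time effects". The next sentence turns to time effects, says they should be "small relative to the differences between the doses in the broad range investigated, unbiased comparisons between treatments can still be expected", and ends there.

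The endpoint is set in section 5.2.1: "Primary endpoint to assess safety and tolerability of BI 1265162 is the number [N (%)] of subjects with drug-related adverse events". Section 5.2.2.2 says who makes the judgement: "The investigator should determine the causal relationship to the trial medication". SAP 7.8.1 builds the primary table on that investigator classification.

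Four places show what the investigator knows:

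- Section 4.1.5.1: treatments "will be single-blind (blinded to subjects only".
- Section 4.1.5.2: "the treatment information will be known", so emergency envelopes are not supplied.
- Section 4.1.2: "The randomization list with study subject numbers and allocated treatments will be provided to the trial site and the sponsor (TCM) in advance".
- Section 7.5: the first cohort of each dose level is not randomised, "to maintain a treatment sequence of active-placebo-active-active due to safety reasons".

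Section 3.2 adds that investigators know the dose level.

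**The concern.** Section 3.2 names two weaknesses, observer bias and time effects. It then offers an argument about the second as if it settled both. The first weakness is the one that reaches the primary endpoint, because a subject counts only when an investigator who knows the allocation calls an event related. Some listed arguments for relatedness in section 5.2.2.1, such as known pharmacology, drug class and dose-response, come to hand more readily for a subject known to be on active drug.

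Section 7.1.1 states the primary objective as a descriptive comparison of active dose groups with placebo, and a descriptive comparison can be biased too. If the sentence were relied on, a reader might take an excess of drug-related events on active as free of attribution bias when the design does not secure this. That suggests three changes: reword section 3.2, show the any-event count beside the primary count, and add exact confidence intervals to both.

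**Working it through.** **Group sizes.** Section 3.1 gives 7 dose groups of 8, each with 6 active and 2 placebo. So 7 × 8 = 56, which matches the planned total, with 7 × 6 = 42 active and 7 × 2 = 14 pooled placebo. Section 7.6 says the size does not come from a power calculation, so no power or error rate is at stake.

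**Does the conclusion follow for the primary endpoint?** Set time effects and the drug effect to zero. Let *p* be the risk of any adverse event, equal in both arms. Let *a* and *b* be the probabilities that an event is judged related on active and on placebo. Counting at most one event per subject for simplicity, the apparent difference is *p* × (*a* − *b*) and the apparent ratio is *a*/*b*. The documents give none of these inputs, so the values below are assumptions across a range.

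| *a* v *b* | *p* = 20% | *p* = 40% | *p* = 60% | ratio |
|---|---|---|---|---|
| 50% v 50% | 0 points | 0 points | 0 points | 1.00 |
| 50% v 40% | 2 points | 4 points | 6 points | 1.25 |
| 50% v 25% | 5 points | 10 points | 15 points | 2.00 |
| 70% v 20% | 10 points | 20 points | 30 points | 3.50 |

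For example, 0.40 × (0.50 − 0.25) = 0.10. Differential attribution alone can create a difference while time effects are nil, so small time effects are not enough. The table shows what could happen; it is not evidence that it will.

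**What would each change alter?**

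- *Rewording section 3.2.* No endpoint, analysis set, model, table or escalation rule refers to the sentence. Section 3.1 bases escalation on all available safety data. Deleting the conclusion outright would also remove it where it is better founded: ECG intervals are read centrally by staff blinded to treatment and time point (section 4.1.5.1), and plasma concentrations come from a validated assay (section 5.5.3.1). Neither depends on causality judgement.
- *Any-event count beside the primary count.* SAP 7.8.1 already tabulates subjects with any adverse event by treatment, and drug-related events separately. Placing them side by side is a matter of layout.
- *Exact intervals.* These describe imprecision. With no events, the upper 95% limit is 1 − 0.025^(1/6) = 45.9% for a dose group and 1 − 0.025^(1/14) = 23.2% for pooled placebo. Section 7.2 says intervals will be computed but names no endpoint. SAP 7.8.4 supplies them for the ECG model, and blanked text in section 7.1.1 and SAP 7.5.2 may hold others. Nothing visible requires them for event counts.

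**Figures that do not measure the bias.** Reclassifying one subject moves a dose group by 1/6 = 16.7 points and pooled placebo by 1/14 = 7.1 points. Those steps, like the limits above, would be identical under full double-blinding. The fixed first cohorts cover 7 × 4 = 28 of 56 subjects, but the site holds the list for everyone, so they add nothing to what the investigator knows.

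**The case for a change.** The best argument for a change is that the fault lies in the conclusion, not in the disclosure. A protocol that admits observer bias and then sets it aside with a reason that does not apply is arguably worse than one that stops at the admission. The sponsor blinded the ECG readers, so it knew how to blind an assessor, yet the visible text describes nothing similar for the primary endpoint. The repair would be a sentence, with no new data and no new endpoint.

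The logical point stands: for drug-related events, the reason given does not support the conclusion. It does not follow that the plan must change. The sentence opens with time effects and compares them with differences between doses, so it can fairly be read as answering the time half of the stated disadvantage. Unblinded assessment is disclosed in several sections. Exposure is reduced, though not removed, because subjects do not know whether they receive active or placebo, event questions are non-specific, and arguments for and against causality are written down. Using dose-response as one of those arguments is prescribed by the protocol and is not in itself bias.

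The cost is also more than a sentence, since changing section 3.2 takes a protocol amendment. Amendment 2 already concerns dose group 7, the last of the seven planned, so new rationale wording would alter little in conduct.

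**Conclusion.** The wording in section 3.2 is looser than it should be for one endpoint, but no change to the plan follows. The size and direction of any attribution bias cannot be derived from the documents. Under the assumed attribution rates the apparent difference runs from 0 to 30 points, and revised rationale wording would leave it exactly where it is. No hypothesis is tested, the observer bias is disclosed, and the any-event comparison that bypasses attribution is already planned, although unblinded staff still collect those events. Confidence intervals would quantify imprecision without touching the bias.

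A statistician writing the trial report would say that causality was assessed unblinded and would read the drug-related table with the any-event table. This conclusion rests on the analysis staying descriptive and on both tables being reported whatever they show.
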